How are your sinus symptoms (scale of 1 to 6)? (circle one) 1 a lot worse, 2 a little worse, 3 the same, 4 a little better, 5 a lot better, or 6 no symptoms

SNOT-16

Rate how much you have been bothered, in terms of severity and frequency, by the following symptoms on a scale of 0=no problem, 1=mild or slight problem, 2=moderate problem, or 3=severe problem

- 1. Need to blow nose:
- 2. Sneezing:
- 3. Runny nose:
- 4. Cough:
- 5. Postnasal discharge:
- 6. Thick nasal discharge:
- 7. Ear fullness:
- 8. Headache:
- 9. Facial pain or pressure:
- 10. Wake up at night:
- 11. Lack of a good night's sleep:
- 12. Wake up tired:
- 13. Fatigue:
- 14. Reduced productivity:
- 15. Reduced concentration:
- 16. Frustrated, restless, or irritable:

Do you have any side effects? (circle or check)

- 1. Diarrhea: 0 none, 1 mild, 2 moderate, 3 severe
- 2. Abdominal pain: 0 none, 1 mild, 2 moderate, 3 severe
- 3. (For women) vaginal discharge and itching: 0 none, 1 mild, 2 moderate, 3 severe
- 4. Rash: [] rash without itching [] rash with itching (or hives)
- 5. Other:

E. DATA COLLECTION FORM

See attached. (Each day—enrollment, day 3, day 10, and day 30--will be on a separate sheet of paper.)

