Note that, unlike the IDSA guidelines, (2012) we do not plan automatically to treat with high-dose amoxicillin/clavunate all patients >65 or those who were hospitalized recently but not treated with antibiotics.

- 8. Suspicion of MRSA.
- 9. Drug warnings
 - a. Chronic kidney disease with estimated GFR < 30;
 - b. Hepatic impairment (not including isolated transaminase elevation <2 times normal);
 - c. Current mononucleosis (because of amoxicillin-induced rash);
 - d. History of antibiotic-associated colitis.
- 10. Need to hospitalize because of severity of infection, respiratory distress, or vulnerability of patient.

Treatment arms

- 1. Amoxicillin/clavulanate 1000/62.5 ER 2 tabs po bid for 7 days. (total pill burden 4 per day)
- 2. Amoxicillin/clavulanate 875/125 tabs 1 tab + 1 placebo tab po bid for 7 days (total pill burden 4 per day).

The duration of 7 days is in accordance with IDSA guidelines.

Both groups would be advised: 1) to instill saline into each nostril at least 2 times a day (1/4 tsp salt dissolved in 4 oz of distilled or boiled water, 1 teaspoonful administered into each nostril by sniffing, by syringe, or by Neti-pot; 2) to take acetaminophen for discomfort (not to exceed a total daily dose of 3 grams, or 2 grams if the patient drinks ETOH).

The pharmacist would prepare the medication bottles and randomize them (i.e., number the two sets of medication bottles as determined by a random number generator and keep the list of correlations between bottle number and actual contents).

Measurements (clinical)

- 1. Diagnostic criteria for acute sinusitis (as listed above): clinician to record these (including duration of illness and the category of acute sinusitis)
- 2. Initial additional data collection by nurse or clinician: previous side effects with antibiotics, antibiotics within past month, hospitalization in past 5 days, comorbidities (e.g., diabetes, heart disease, and lung disease)
- 3. Sinonasal Outcome Test-16 (SNOT-16) at days 0, 3, 10, and 30 (for validation of the form, see Garbutt et al, 2011, and Quadri et al, 2013).
- 4. Patients' summary assessment of their condition at days 3, 10, and 30: a lot worse, a little worse, the same, a little better, a lot better, no symptoms (as used by Garbutt et al, 2012).
- 5. Side effects at days 3 and 10
 - a. Diarrhea: none, mild, moderate, severe
 - b. Allergic reaction: rash without itching, rash with itching or hives
 - c. Other: abdominal pain, vaginal discharge and itching, other

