6. Drop outs:

- a. The participant can exit the study at any time, if much sicker, by going to the emergency department
- b. The participant can request, at any time, treatment with open-label antibiotic, e.g. doxycycline or levofloxacin (recommended by the IDSA), at the discretion of the clinician in the office or on call.
- c. The participant will be formally given this option at the day 3 telephone call.
- 7. Participants will be asked additionally at day 10
 - a. To guess which treatment they took (to evaluate adequacy of blinding, although it is expected that patients who get better faster will assume they took the higher dose).
 - b. To indicate how many doses they took. We will not ask for the bottles to be returned (which would require an otherwise unnecessary office visit for the participants).
 - c. To indicate if they would take that particular medication again if prescribed.
- 8. Participants will be asked additionally at day 30 if, and to what extent, they had persistence, resolution, or recurrence of symptoms.

Measurements (bacteriological)

Nasal cultures (anterior) will be performed on every patient. The cultures will be processed at the Albany Medical Center microbiology laboratory to assess:

- 1. What pathogens are present?
- 2. If S. pneumonia, what is its level of penicillin resistance?
- 3. If S. aureus, is it methicillin resistant?

Endpoints

- 1. Primary endpoint: Major mprovement of subjective symptoms at day 3 (i.e., 48-72 hours after starting treatment), rated as "a lot better" or "no symptoms."
- 2. Secondary clinical endpoints:
 - a. At least mild improvement in subjective symptoms at day 3: percent in each group rating their condition as "a little better," "a lot better," or "no symptoms"
 - b. Improvement in SNOT-16 score at day 3. Garbutt et al. (2012) indicate that a minimally important difference is 0.5 (on a scale of 0-3), although they used an effect size of 0.25 for their study size determination (requiring a bigger sample size). We will compare the percent in each group with average improvement \geq 0.5
 - c. The same comparisons at days 10 and 30 (one month).
 - d. Comparisons of side effects—diarrhea and others mentioned by participants on scale of 0=none to 3=severe--at days 3 and 10.
 - e. Percent of who dropped out because of side effects or inefficacy (switched to alternative antibiotic or went to the ED).

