- 12. The clinician or the nurse collects the completed SNOT-16 and gives the patient a handout with instructions on additional measures, in particular on nasal saline preparation and use and on acetaminophen dosing.
- 13. The clinician or nurse also gives the patient a copy of the questions that will be asked at the day 3 telephone call and requests the patient to fill it out at the specified time (between 48 and 72 hours after starting treatment) if, for any reason, the patient cannot be reached by telephone. If needed, the resident co-investigators will then arrange with the patient how to obtain this form.
- 14. The clinician fills out the Data Collection Form for day O. This and the SNOT-16 will be scanned into the EHR (they will serve as documentation of at least part of the office visit) and put into the study binder and kept in a locked drawer in the PIs office (clinicians will have access to the key).
- 15. The clinician enters into the EHR a diagnosis of acute sinusitis, a treatment of amoxicillin/clavulanate (without specifying the dose), and an indication in the office visit note that the patient is a study participant.
- 16. The nurse prepares the culturette in accordance with the procedure agreed on with AMC clinical pharmacology lab.

Follow-up

- 17. The resident co-investigators prepare, in collaboration with the residency coordinator and the residency team's PA, a list of residents (or medical students) responsible for telephone follow-up each day. They make sure—through word-of-mouth, telephone calls, secure texting (using Cureatr), or secure AMC email—that the resident or medical student calls each patient at 3 days, 10 days, and 30 days and fills out the appropriate Data Collection Form. They may look into setting up a secure Google Group site where the lists can be kept and accessed. The resident co-investigators make sure that the completed Data Collection Forms for each patient are inserted into the patient's study binder.
- 18. If the patient reports clinical worsening or bad side effects, the resident or student notifies the clinician on call (or, if more appropriate, the clinician at the office the next day).
- 19. If the participant calls at any time to report a clinical worsening or bad side effects, or if the participant reports this at the 3 days telephone call, the clinician involved can decide, along with the participant:

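### The global rating item names no reference point, so at days 10 and 30 (secondary endpoints) stable early improvers could be counted as not improved

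*Combined protocol and SAP*

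**What the plan says.** The item is printed on a question sheet in the appendix, just before the entry for the Data Collection Form. The stem is "How are your sinus symptoms (scale of 1 to 6" and the answers are "1 a lot worse, 2 a little worse, 3 the same, 4 a little better, 5 a lot better, or 6 no symptoms". Answers 1 to 5 are comparative; only answer 6 describes a state.

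Section B, Measurements (clinical), item 4, lists the patients' "summary assessment of their condition at days 3, 10, and 30" with the same six categories and no comparator. Under Endpoints, the primary endpoint is "Major mprovement of subjective symptoms at day 3 (i.e., 48-72 hours after starting treatment", met by either of the top two categories. Item 2a adds the 'a little better' category at day 3, and item 2c extends the set: "The same comparisons at days 10 and 30 (one month".

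The ratings are taken by telephone. Under Procedure, Follow-up, step 17, a resident or student "calls each patient at 3 days, 10 days, and 30 days and fills out the appropriate Data Collection Form". At enrolment (step 13) the clinician or nurse "gives the patient a copy of the questions that will be asked at the day 3 telephone call".

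**The concern.** A change scale needs a stated starting point. By day 10 the patient has already given a rating at day 3, and by day 30 a second one at day 10. Someone who was 'a lot better' at day 3 and has been stable since, with some symptoms left, can truthfully answer 'the same' at day 10. Under item 2c that patient fails both the major-improvement and the at-least-mild-improvement comparison, although nothing has been lost since treatment began.

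The error need not be equal between arms. It falls on early responders, and the trial's hypothesis is that high dose produces more of them. If that is true, the later comparisons would understate a lasting benefit, or show a late disadvantage that does not exist. It cannot be repaired afterwards, because nothing in the plan records which comparator each patient used.

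**Working it through.** **1. Is there an anchor anywhere in the available text?**

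| Place | Comparator stated? |
|---|---|
| Appendix question sheet, stem and answers | No |
| Measurements (clinical), item 4 | No |
| Endpoints 1, 2a, 2c | No; endpoint 1 gives the time of rating in relation to treatment start, not the comparator |
| Procedure, steps 13 and 17 | No instruction to callers on a comparator |
| Day 3, 10 and 30 data collection forms | Attached separately, not seen |

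The printed sheet is probably the patient's copy of the day 3 questions. It lacks the extra day 10 questions (treatment guess, doses taken, willingness to take the drug again) listed under Measurements, item 7.

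**2. The plan's own figure.** Inputs from Sample size determination: 34% and 50% at day 3, 80% power, alpha 0.05.

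n = [0.34 × 0.66 + 0.50 × 0.50] × (1.960 + 0.842)² / 0.16² = 0.4744 × 7.849 / 0.0256 = 145.4, rounded up to 146 per group.

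This reproduces the stated 146 as a two-sided calculation. Power at the planned 150 per group is 80.5%. Both rest on day 3 only, so an anchor changes neither.

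**3. Shift at a later call.** The assumptions below are not document figures:
- every day 3 responder is still a responder relative to day 0;
- a share r of them has residual symptoms, since those with none can choose the absolute answer 6;
- a share q of that group compares with the last call and no longer rates 'a lot better';
- r and q are the same in both arms.

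With true later rates H (high dose) and R (regular dose):
- observed high dose = H − 0.50 × r × q
- observed regular dose = R − 0.34 × r × q
- observed difference = (H − R) − 0.16 × r × q

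| r | q | Shift against high dose (points) |
|---|---|---|
| 0 | any | 0 |
| 0.25 | 0.25 | 16 × 0.0625 = 1 |
| 0.5 | 0.5 | 16 × 0.25 = 4 |
| 0.5 | 1 | 16 × 0.5 = 8 |
| 1 | 1 | 16 (extreme bound) |

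**4. What such a shift could do.** Purely for illustration, take 74% and 56%, the day 7 amoxicillin and placebo rates that the background quotes from the earlier adult trial. With 150 per group and a two-sided 0.05 test:

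| Case | Observed rates | Difference (points) | Power |
|---|---|---|---|
| No mis-anchoring | 74% vs 56% | 18 | 90.9% |
| r = q = 0.25 | 70.9% vs 53.9% | 17 | 86.3% |
| r = q = 0.5 | 61.5% vs 47.5% | 14 | 68.4% |

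If instead both arms truly reach 74%, r = q = 0.5 gives 61.5% vs 65.5%, a spurious deficit of 4 points for high dose.

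The model covers early responders only. Patients who improve in steps, a little by day 3 and a little more by day 10, could also be misclassified, and the documents give no rates from which to judge how that would fall between the arms.

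**The case against.** The strongest reply is that the forms actually used at days 10 and 30 have not been seen. The protocol refers to them as attached, one sheet per contact, and a stem or caller script there might supply the anchor. A reader might infer that the plan has no anchor at any contact; the documents do not support that. What stands is that the one patient-facing wording available has none, and the measurement list gives the same unanchored scale for all three days.

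A reader might also infer that the primary endpoint is biased, because it uses this item. The documents do not support that either. No study call precedes day 3, and the rating is timed from the start of treatment, which is the comparator a patient would naturally use.

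The plan contains partial safeguards. Answer 6 is absolute, so patients who remain symptom-free are not penalised, and the effect should shrink by day 30 if most have recovered. The "Sinonasal Outcome Test-16 (SNOT-16) at days 0, 3, 10, and 30" supplies a measure with a recorded baseline. Day 30 also asks whether symptoms lasted, cleared or came back, and Other questions, item 4c, correlates SNOT-16 change with the global rating. These are useful cross-checks. They do not replace the global-rating comparison, and the item 4c correlation would itself be blurred if the rating is not anchored to day 0.

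**Conclusion.** The missing reference point is confirmed in the available text. It matters for the secondary global-rating comparisons at days 10 and 30, and hardly at all for the day 3 primary endpoint or the sample size. The direction is conditional: it works against high dose only if more high-dose patients improve early, keep some symptoms, and then compare with the last call.

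The size is unknown. Under the stated assumptions it is 16 × r × q points, from 0 to 1 to 4 points at the settings r = 0, r = q = 0.25 and r = q = 0.5, and the range must include zero.

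A reader might apply a flat loss of, say, 10 to 30% to all day 3 responders, giving 16 × 0.1 = 1.6 to 16 × 0.3 = 4.8 points, and present the resulting fall in day 10 power as a defect of the trial. That goes too far. No such share appears in the documents. It would include patients who are already symptom-free. The 74% and 56% are day 7 rates for a different comparison, measured on the same scale, and may already contain any mis-anchoring. The trial was also not powered for day 10, so no planned power is being missed. This is a cheap improvement to a secondary outcome.

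**What to change.** Before enrolment, word the item on the patient sheet, the data collection forms and the call script, at days 3, 10 and 30, as: 'Compared with the day you started the study medicine, your sinus symptoms are ...'. State the same comparator in Measurements (clinical), item 4, and in the endpoint definitions. If the attached day 10 and day 30 forms already carry an anchor, copy it to those places.

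The cost is a few words. Sample size, calls and visits do not change. The one downside is slightly reduced comparability with the earlier adult trial's rating, if its wording differed.

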The purpose of the study is, using study procedures duplicating in large part those of Garbutt et al (2012), to compare the benefits of 2 treatment arms—high-dose amoxicillin/clavulanate (2000 mg amoxicillin/125 mg po bid) vs regular-dose amoxicillin/clavulanate (875 mg amoxicillin/125 mg po bid)--at day 3 (primary endpoint) and day 10 (secondary endpoint), by reported degree of improvement (primary endpoint, as in Wald et al., 2009) and by SNOT-16 (secondary endpoint, but which was the primary endpoint in Garbutt et al, 2012). We will use amoxicillin/clavulanate, rather than amoxicillin alone, to be in accord with the IDSA 2012 guideline (IDSA, 2012). The duration will be 7 days in line with the IDSA guidelines. We will not have a pure placebo arm since 1) the IDSA guidelines recommend treatment; 2) clinical studies (Wald et al, 1986; Bucher et al., 2003) suggest that treating with the IDSA-recommended regular-dose amoxicillin/clavulanate is equivalent, or almost equivalent, to giving a placebo; 3) we will not exclude patients who we would not want to risk giving a true placebo; and 4) we know that, because of patients' continued belief in the efficacy of antibiotics, recruitment will be easily in a study with two treatment arms, rather than treatment and placebo arms. In addition, we will study whether the response to antibiotics can be predicted by the presence or not of penicillin-resistant S. pneumoniae in the nasopharynx.

Thus the study questions are: 1. Is high-dose amoxicillin/clavulanate superior to regulardose in improving the clinical symptoms of presumed sinusitis? 2. Does the higher dose result in increased incidence and/or severity of adverse effects, such as diarrhea? 3. Does the resistance pattern of S. pneumonia in nasopharyngeal cultures predict response to antibiotic treatment? The hypotheses are yes for #1, no for #2, and no for #3 (but with the expectation of insufficient power to answer question #3).

B. Study Design

Study type: randomized, double-blind clinical study with two active treatment arms

Location: AMC Internal Medicine and Pediatrics office in Latham, NY

Duration: 2 years; each participant will be in the study for 30 days.

Subjects:

Inclusion criteria

1. Adults age 18 and over. The study on children already indicates a benefit of high-dose amoxicillin-clavulanate over placebo. The restriction to adults eliminates the need for parental consent.

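### The one side-effect question shown has no recall period or worst grade, although study question 2 asks about incidence; and rash and 'Other' lack the 0–3 grade that endpoint 2d uses

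*Combined protocol and SAP*

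**What the plan says.** The second study question under Purpose of Current Study is "Does the higher dose result in increased incidence and/or severity of adverse effects, such as diarrhea", and the stated hypothesis is no.

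Measurements (clinical), item 5, schedules "Side effects at days 3 and 10". The extra day 10 questions (item 7) cover the treatment guess, doses taken and willingness to take the drug again. The extra day 30 question (item 8) covers the course of symptoms. Neither adds side-effect recall.

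The only question wording in the document is in the appendix questionnaire: "Do you have any side effects? (circle or check". Diarrhea, abdominal pain and vaginal symptoms each get one grade from 0 to 3. Rash has two tick boxes by type, and 'Other' is a blank line. The sheet carries no visible day label. It fits Procedure, Enrollment, item 13, where the patient receives "a copy of the questions that will be asked at the day 3 telephone call", to be completed 48 to 72 hours after starting treatment. The Data Collection Form heading says that each day has its own sheet, and those sheets are attached but not shown.

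Secondary endpoint 2d compares diarrhea and other effects "mentioned by participants on scale of 0=none to 3=severe--at days 3 and 10". Section D leaves the analysis of secondary outcomes to the statistician and names no effect measure.

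**The concern.** Incidence means that an effect occurred at any time on treatment. A present-tense item with a single grade, answered as written, gives status at the moment of the call. An effect that started on day 1 and was gone by the call would be recorded as none, and one that had eased would be recorded at its milder grade.

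If both arms lose the same share, the observed risk difference shrinks toward zero, which is the direction of the hypothesised answer, and its upper limit falls too. The risk ratio keeps its expected value but its interval widens. Since no scale is named, how under-capture would read depends on a choice made later.

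A second problem needs no assumption about how people answer. Endpoint 2d is defined on a 0–3 grade, but Measurements item 5b records "Allergic reaction: rash without itching, rash with itching or hives", which is a type, and the questionnaire does the same. 'Other' has no grade either.

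**Working it through.** **1. The plan's own figures.** The plan gives none for side-effect capture or safety power. Its 146 per group is for the primary endpoint and reproduces with the unpooled two-sided formula: (1.95996 + 0.84162)² × (0.34×0.66 + 0.50×0.50) / 0.16² = 7.849 × 0.4744 / 0.0256 = 145.45, rounded up to 146. The planned 150 per arm is used below.

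**2. Share of effects captured (all assumed).** Onset falls within the 7 treatment days, either uniform or early (exponential, mean 2.5 days, truncated at 7). Duration is exponential with mean 1 to 5 days, or fixed at 7 days. The first call is uniform over 48–72 hours and the second is at day 10. The item is answered literally at day 3. Results come from 1,000,000 simulated episodes.

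Hand check for uniform onset, mean duration m = 1 day, call at c = 2.5 days: begun by the call, c/7 = 0.357; still present, (m/7)(1 − e^(−c/m)) = 0.131; settled, 0.357 − 0.131 = 0.226, or 63% of those begun.

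| Onset, duration | Settled before day 3 call, % of all | % of those begun by then | Captured if day 10 asks since the last call | Captured if day 10 repeats the present tense |
|---|---|---|---|---|
| Uniform, mean 1 d | 22.7 | 63.4 | 77.3 | 13.8 |
| Uniform, mean 5 d | 7.7 | 21.5 | 92.3 | 51.2 |
| Early, mean 1 d | 46.8 | 69.9 | 53.2 | 20.4 |
| Early, mean 5 d | 16.5 | 24.7 | 83.5 | 60.9 |
| Either, fixed 7 d | 0 | 0 | 100 | 93 |

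If day 10 asks about everything since starting, capture is about 100% in every row, apart from recall error.

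**3. Effect on the comparison.** Section E, Risks of treatment, item 4 cites diarrhea in 16.7% (high dose) and 14.4% (standard dose). Treat these as full capture, with 150 per arm and capture share f equal in both arms.

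- Risk difference = f × (0.167 − 0.144).
- Half-width = 1.96 × √[(p₁(1−p₁) + p₀(1−p₀))/150], with p₁ = 0.167f and p₀ = 0.144f. At f = 1: 1.96 × √(0.2624/150) = 0.082.
- Risk ratio = 0.167/0.144 = 1.16 for every f. Its log standard error is √[(1−p₁)/(150p₁) + (1−p₀)/(150p₀)], which is 0.270 at f = 1.

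| Capture f | Expected cases, standard vs high | Risk difference, points | Upper 95% limit, points | Risk ratio 95% CI | Power |
|---|---|---|---|---|---|
| 1.00 | 21.6 vs 25.1 | 2.3 | 10.5 | 0.68–1.97 | 8.5% |
| 0.77 | 16.6 vs 19.3 | 1.8 | 9.1 | 0.63–2.15 | 7.6% |
| 0.61 | 13.2 vs 15.3 | 1.4 | 8.0 | 0.58–2.34 | 7.0% |
| 0.53 | 11.4 vs 13.3 | 1.2 | 7.4 | 0.54–2.47 | 6.7% |
| 0.14 | 3.0 vs 3.5 | 0.3 | 3.6 | 0.25–5.31 | 5.4% |

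Even the largest shift in the risk difference, 2.3 − 0.3 = 2.0 points, is well inside the full-capture half-width of 8.2 points. For a larger harm the loss would count for more. If the higher dose doubled diarrhea (14.4% to 28.8%, an assumption without support in the documents), power would be 86% at full capture and 52% at 50%.

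**4. Endpoint 2d against the form.** The endpoint needs a grade from 0 to 3. Diarrhea, abdominal pain and vaginal symptoms have one; rash and 'Other' do not. No arithmetic is involved.

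**The case against.** The strongest objection is that much of the possible loss depends on sheets that are not available. The day 10 sheet may contain recall wording, and so may the text just before the questionnaire, which is also not available. Neither can be counted as missing from the plan. This stands, and it limits the point to the wording shown and to the protocol text, which states no recall period.

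Next, a first call 48 to 72 hours into treatment invites an answer about the course so far, and the SNOT-16 stem on the same sheet is not strictly present tense. Some participants will answer cumulatively. That reduces the expected loss but leaves the item open to two readings, which callers and patients may resolve differently.

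Third, endpoint 2d can be read as status at two time points, which the item would serve. That is fair for 2d, but study question 2 asks about incidence, and a status measure does not answer it.

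Fourth, consequential effects have other routes. Follow-up item 19 provides for action "If the participant calls at any time to report a clinical worsening or bad side effects", and endpoint 2e is "Percent of who dropped out because of side effects or inefficacy". This stands: what is exposed is mainly transient mild or moderate effects.

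A reader might infer that the trial will miss most side effects, or capture as few as 14%. The documents do not support that. The figure needs the unseen day 10 sheet to repeat the present tense, strictly literal answers, uniform onset and a mean duration of 1 day, all at once.

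**Conclusion.** The point holds in limited form. The wording shown, answered literally, measures what is present at the call and not the incidence that study question 2 asks about. At day 3 it misses effects that have already settled. Whether anything between day 3 and day 10 is lost cannot be determined from the documents.

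The size of the loss is unknown: every capture figure rests on assumed onset, duration and literal answering, and the range includes no loss at all. Nor do the documents support the inference that this item would by itself produce a false finding of no added harm. At the cited diarrhea rates the comparison has under 9% power even with perfect capture, and equal under-capture leaves the expected risk ratio at 1.16.

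The mismatch between endpoint 2d and the ungraded rash and 'Other' items is certain on the sheet shown. The label 'day 3' for that sheet is an inference from Enrollment item 13. Severity is minor: one secondary safety question is affected, and the primary endpoint is not.

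**What to change.** Use the same wording at both calls, for example: *Since starting the study medicine, have you had any of these, and how bad was it at its worst (0–3)?* Asking day 10 only about the time since the last call would be weaker. Enrollment item 13 foresees patients who cannot be reached by telephone at day 3; if their form is not recovered either, that anchor is undefined or drops the first three days. With a since-starting question, a missed day 3 call loses nothing.

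Add a 0–3 worst grade for rash, keeping its type, and for 'Other'. State the recall period in Measurements item 5 and endpoint 2d. In section D, name the comparison: cumulative incidence to day 10 by arm, as a risk difference and a risk ratio, each with a 95% confidence interval.

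If the attached forms already carry a since-starting recall period, keep it and write it into the protocol.

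The cost is a change of form wording and about a minute on calls already planned, with some recall error over up to 10 days. No extra contacts are needed.

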- 2. Research assistant (coordinator if possible) (if the resident on medical home rotation or a work-study student is not a feasible option)
 - a. Telephoning patients: 1 hour per patient x 300 patients @ \$20 per hour = \$6,000
 - b. Entering data: 100 hours a \$20 per hour = \$2,000.
- 3. Statistician: 20 hours @ \$100 per hour = \$2,000.
- 4. Cultures: estimate of \$100 per culture= \$30,000.
- 5. Duplication of forms: 600 @ 10 cents = \$60.
- 6. Study binders: 300 @ 50 cents = \$150.
- 7. Overall cost: \$44,550.
- 8. Funds will come from the AMC Med-Ped Research Fund, derived from private contributions and held by the Albany Medical Center Foundation, at the discretion of the Medicine-Pediatrics Division Head (currently [name]).

C. Subject Population

Source of participants: the patients of AMC Internal Medicine and Pediatrics, [name], who present with respiratory symptoms.

Total number of participants to be enrolled: 300.

Characteristics of population: adults, with no special populations (see Inclusion and Exclusion criteria above).

D. Data Analysis

See the Data Collection Sheet for a listing of the data that will be collected.

The Data Collection Sheets will be stored in a locked drawer in the PI's office.

The data will be entered by the research assistant (or Med-Ped residents or medical students doing work-study) into an Excel data base stored on a password-protected computer in the PI's office.

The Excel data base will be stripped of patient identifiers and transferred to SPSS by the statistical consultant, [name], who will, in turn, perform the analyses.

The primary analysis will be a simple chi-square analysis, with an alpha of .05%, of the difference in the primary endpoint (the proportion of participants who are "a lot better" or "no symptoms" at 3 days).

The analyses of the secondary outcomes (listed above) will depend on the nature of the data and be determined by the statistician.

E Risks

Risks of treatment

The side effects of treatment with amoxicillin/clavunate include:

- 1. Allergic reaction, usually minor, sometimes severe enough to send to the ED, very rarely resulting in death. Wikipedia's entry on anaphylaxis suggests death in about 1 out of 50,000 courses of penicillin.

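### Item 18 lets a caller who is not a clinician decide whether a new rash or hives reaches a clinician; separately, the questionnaire's Other line lacks the grade endpoint 2d uses

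*Combined protocol and SAP*

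**What the plan says.** All references are to the combined protocol and SAP.

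- **Escalation.** Procedure, Follow-up, item 18: "If the patient reports clinical worsening or bad side effects, the resident or student notifies the clinician on call", or the office clinician the next day if that is more appropriate. Item 19 then leaves management to the clinician and the participant.
- **Who calls.** Item 17: "the resident or medical student calls each patient at 3 days, 10 days, and 30 days". Costs, item 2, adds a research assistant if a resident or work-study student is not feasible: "Telephoning patients: 1 hour per patient x 300 patients". Section G, item 2, counts residents among the clinicians and lists medical student research assistants separately.
- **Side-effect recording.** Measurements (clinical), item 5b: "Allergic reaction: rash without itching, rash with itching or hives". The appendix questionnaire has the same two types as tick boxes: "Rash: [] rash without itching [] rash with itching (or hives". It prints a 0 to 3 grade for diarrhea, abdominal pain and vaginal symptoms. The Other line is blank.
- **Endpoint.** Endpoints, 2d, compares side effects at days 3 and 10: "diarrhea and others mentioned by participants on scale of 0=none to 3=severe". This serves study question 2: "Does the higher dose result in increased incidence and/or severity of adverse effects, such as diarrhea".

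**The concern.** There are two separate points.

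The first concerns participant safety. Whether a rash or hives is passed on depends on the caller finding it bad. The protocol neither defines that word nor names rash or hives as a trigger. A student or assistant who hears that the sinuses are much better, but that there is an itchy rash, can follow item 18 to the letter without telling a clinician. The protocol itself takes drug reactions seriously. Section E describes allergic reactions as occasionally needing emergency care and very rarely fatal, and the exclusion criteria remove allopurinol users and people with current mononucleosis because of rash. These exclusions, with the penicillin-allergy exclusion, lower the risk but do not remove it.

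The second concerns data for a secondary endpoint. Endpoint 2d names effects that participants mention themselves, and the Other line is where these would be written. Without a grade, the severity comparison for them has no data, and a grade not asked for during follow-up may not be recoverable later.

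**Working it through.** The plan gives no figure on this point, so there is none to reproduce. The check is a comparison of sections plus one dose count.

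**1. Who may hear of a rash, and what item 18 asks of them**

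| Caller | Source | Duty to pass on a rash |
|---|---|---|
| Resident | Item 17; a clinician under section G, item 2 | A clinician already knows |
| Medical student | Item 17 | Only if judged bad |
| Research assistant | Costs, item 2 (fallback) | Item 18 does not name this role |

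The gap is confined to the second and third rows. If a participant cannot be reached at day 3, item 13 says "the resident co-investigators will then arrange with the patient how to obtain this form". The residents who arrange this are themselves clinicians, so the gap is smaller there.

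**2. Treatment still to come at day 3**

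Inputs: twice-daily dosing for 7 days (Treatment arms) and a day 3 contact 48 to 72 hours after starting (Endpoints, item 1; Procedure, item 13). Assumptions: doses every 12 hours from hour 0, none missed.

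- Total doses: 7 × 2 = 14.
- Before hour 48: hours 0, 12, 24, 36 = 4 doses. Remaining: 14 − 4 = 10, and 10/14 = 71%.
- Before hour 72: hours 0 to 60 = 6 doses. Remaining: 14 − 6 = 8, and 8/14 = 57%.

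By the day 10 call the 7-day course is over, so continued dosing is an issue at day 3 only.

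**3. Endpoint 2d against the visible questionnaire**

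| Item | Recorded as | Usable for 2d |
|---|---|---|
| Diarrhea | 0 to 3 | Yes |
| Abdominal pain | 0 to 3 | Yes |
| Vaginal symptoms | 0 to 3 | Yes |
| Rash | Type: none ticked, without itching, itching or hives | As a category |
| Other | Blank line | Presence only, no grade |

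Three of the five items carry the scale. Rash has a three-level classification that matches Measurements item 5b. Only Other has neither a grade nor a category.

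**The case against.** **Escalation.** Item 18 does oblige the resident or student to report bad side effects, and a sensible caller would probably count hives among them. Item 19 lets the participant call at any time, and Drop outs, items 6b and 6c, allows an open-label antibiotic on request and offers it formally at the day 3 call. The research assistant is only a contingency. Consent pages and the patient handout are not shown and may tell participants to report a rash. All of this stands. A reader might infer that a rash has no route to a clinician, and the documents do not support that. What remains is that, for a non-clinician caller, the route depends on an undefined judgement.

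**Grading.** The questionnaire points to an attached Data Collection Form, which is not shown and may carry a grade for Other; a caller could also write one in. That limits the point to the visible questionnaire, where nothing asks for a grade.

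**Rash.** A reader might also infer that rash cannot be compared between arms because it has no 0 to 3 grade. That goes too far. Recording by type appears in both Measurements item 5b and the questionnaire, so it looks deliberate, and separating itching or hives from plain rash is clinically useful for a penicillin. Section D leaves secondary analyses to the nature of the data, so a categorical comparison is open. Rash incidence, the itching or hives split and withdrawals for side effects (endpoint 2e) can all be compared.

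**Size.** It is tempting to size the problem from the adverse-effect rates of the cited bronchitis study. They do not measure it: the population differs, and effects other than diarrhea include the abdominal and vaginal items that are already graded. The documents give no rash rate.

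**Conclusion.** The point holds in a narrow form and is minor. When the day 3 caller is a medical student or research assistant, the visible text does not ensure that a ticked rash or hives reaches a clinician, although 8 to 10 of 14 doses (57% to 71%) remain. That range assumes 12-hourly dosing with none missed. It describes how much treatment is left, not how often a rash would be missed, which cannot be estimated from the documents.

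On data, one of the five questionnaire items, Other, lacks what endpoint 2d needs. This is conditional on the Data Collection Form not supplying it.

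The primary endpoint is unaffected.

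**What to change.** 1. **Item 18.** Require every caller (resident, student or research assistant) to report any ticked rash or hives box to the treating or on-call clinician, however the participant otherwise feels. The clinician keeps the treatment decision.
2. **Other line.** Print 0 none, 1 mild, 2 moderate, 3 severe beside each Other entry on the questionnaire, and on the Data Collection Form if it is absent there.
3. **Rash.** Keep recording by type and compare it as a category (none, without itching, itching or hives). Adding a 0 to 3 rash grade is optional.

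This changes form and protocol wording only, with no added visits, tests or participants. The downside is a few more calls to the clinician.
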